12.3 Safety Assessments

The description of safety assessments is given below, and the timings of these assessments is given in the Schedule of Assessments. The time points of the safety assessments may change depending on information gained throughout the study, however the total number of safety assessments per volunteer will not be reduced, although unscheduled assessments may be performed at the discretion of the Investigator.

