15.1 Statistical method description

15.1.1 General information

Statistical results will be separately presented for parts A and B.

Demographic, baseline characteristics and data recorded during the study will be summarised using descriptive statistics by treatment (placebo, vaccine taken alone or vaccine combined with adjuvant) and dose group, unless otherwise specified. If relevant additional descriptive graphs can be provided.

Individual data for all included volunteers will be presented as a data listing, sorted by treatment and administered dose level.

For parameters with evaluation before vaccination and in case of re-checked value(s), only the last observation prior to dosing will be used in descriptive and inferential statistics and derivations of other parameter values. After vaccination, only values of scheduled assessments (planned in the protocol) will be used.

For laboratory/clinical parameters for which laboratory/reference ranges will be available, position of parameter values according to ranges will be flagged with the following rule:

- "L" for values lower than laboratory/reference ranges;
- "H" for values higher than laboratory/reference ranges.

In addition, parameter values can be assessed by investigator and flagged as follows in order to determine clinical relevance:

- Normal;
- Abnormal and NCS (Not clinically Significant);
- Abnormal and CS (Clinically Significant).

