15.4.2 Primary endpoint for the two study parts

The primary objective is to evaluate the safety and tolerability of the GBS-NN vaccine for 12 weeks after the first dose of vaccine.

All the included volunteers (including the withdrawal and dropout volunteers) will be evaluated for safety analysis (ITT).

The following endpoints will be evaluated:

- **Local and systemic reactogenicity**

Assessment results will be described according to treatment/dose group and visit.

- **Adverse events**

Adverse events will be coded according to the Medical Dictionary for Regulatory Activity (MedDRA). They will be classified into pre-defined standard categories according to chronological criteria:

- Treatment Emergent Adverse Events (TEAEs): AEs which occur for the first time after the first administration or present before and worsened during vaccine exposure;
- Non-Treatment Emergent Adverse Events (NTEAEs): AEs which occur before the first study vaccine administration (also called "pre-dose event").

TEAEs will be described by relation to study vaccine (for example: definite / probable / possible / unlikely / unrelated) and maximum intensity (for example: mild / moderate / severe) according to treatment/dose group. Descriptive statistics will be characterised by number of TEAEs, number and percentage of volunteers with at least one TEAE (based on ITT). In case of few TEAEs (≤ 5 per study part for example), only a listing will be performed.

Vaccine related TEAEs (*i.e.* definite, probable or possible relationship to study vaccine) will be summarised by MedDRA codes (SOC and PT) and treatment/dose group. In case of few vaccine related TEAEs (≤ 5 per study part for example), only a listing will be performed. TEAEs not related to study vaccine (*i.e.* unlikely or unrelated relationship to study vaccine) will also be summarized by MedDRA codes.

Two distinct listings of TEAEs and NTEAEs will be presented by treatment/dose group, volunteer and MedDRA codes in order to provide more information about adverse events (example: description, duration, time since last administration if applicable, seriousness, any actions taken as concomitant medication or hospitalization).

- **Laboratory tests**

Biochemistry and haematology tests will be performed at V1 (screening), V4 (part A), V5 (part B), V8 (parts A and B) and post-study medical visit (V10 for part A and V20 for part B).

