Parameter values, position according to laboratory ranges (if available) and investigator assessment will be described according to visit for each treatment/dose group. In order to study evolution of parameters after vaccination, parameter values changes from pre- to post-dose visits will be performed. Emergent values (for parameters with available laboratory ranges) with their corresponding position according to ranges will be listed by treatment/dose group and volunteer.

- **Urinalysis**

Urinalysis will be performed at V1 (screening), V4 (part A), V5 (part B), V8 (parts A and B) and post-study medical visit (V10 for part A and V20 for part B).

Parameter values (quantitative or binary results, *i.e.* positive/negative), position according to laboratory ranges (if available) and investigator assessment will be described according to visit for each treatment/dose group. In order to study evolution of continuous parameters after vaccination, parameter values changes from screening to post-study medical visit will be performed. Emergent values (for parameters with available laboratory ranges or with binary results) will be listed by treatment/dose group and volunteer.

- **Vital signs**

Vital signs will be characterised by heart rate, blood pressure, tympanic temperature and respiratory rate. Vital signs will be assessed at V1 (screening), V2 (pre-dose, T2h and T3h post-dose), V3, V4 (part A only), V6 (pre-dose and T2h post-dose for volunteers receiving booster dose), V7 (only if administered booster dose), V8, and post-study medical visit (V10 for part A and V20 for part B). For study part B, additional vital signs assessments will be performed at V5, V8, V9, V10, V11, V13, V15 and V17.

Parameter values, position according to reference ranges (if available) and investigator assessment will be described according to visit and assessment time for each treatment/dose group. In order to study evolution of parameters after vaccination, parameter values changes from pre-dose to post-dose assessments will be performed. Emergent values (for parameters with available reference ranges) with their corresponding position according to reference ranges will be listed by treatment/dose group and volunteer.

- **12-lead ECG parameters**

ECG will be assessed at V1 (screening) and post-study medical visit (V10 for part A and V20 for part B).

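### The scheduled-values-only rule has no exception for emergent values, so unscheduled out-of-range results that are not AEs would drop out of the primary-endpoint emergent listings

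*Combined protocol and SAP*

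**What the plan says.** Section 15.1.1 sets general data-handling rules for both study parts. Before vaccination, where a value has been re-checked, "only the last observation prior to dosing will be used in descriptive and inferential statistics and derivations of other parameter values". The next sentence covers the period after vaccination: "After vaccination, only values of scheduled assessments (planned in the protocol) will be used". It carries no qualification.

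Section 12.3 foresees data outside the schedule. It says that the number of planned safety assessments will not be reduced, "although unscheduled assessments may be performed at the discretion of the Investigator".

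Section 15.4.2 describes the primary endpoint, whose objective is to "evaluate the safety and tolerability of the GBS-NN vaccine for 12 weeks after the first dose of vaccine". For laboratory tests it plans this output: "Emergent values (for parameters with available laboratory ranges) with their corresponding position according to ranges will be listed by treatment/dose group and volunteer". For vital signs, and in the same words for ECG, it plans: "Emergent values (for parameters with available reference ranges) with their corresponding position according to reference ranges will be listed by treatment/dose group and volunteer". Urinalysis has a similar listing that also covers positive/negative results. None of these paragraphs mentions unscheduled values.

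**The concern.** Using scheduled values only is ordinary practice for by-visit summaries and tests. It keeps extra measurements on a few volunteers from distorting the visit means. An emergent-value listing has a different purpose: to show every volunteer whose value moved out of range after vaccination, whenever that was seen. A rule suited to the first output is written so that it also reaches the second.

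Safety over 12 weeks is the primary objective, and Section 6.3 states that the vaccine has not previously been given to humans. What is at stake is the completeness of the emergent listings that support that objective, particularly for assessments scheduled rarely or not at all within the window.

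**Working it through.** The plan attaches no figure to this rule, so there is nothing to reproduce. The check sets the sections side by side and counts scheduled assessments.

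**Step 1: does the rule reach the emergent outputs?** The scheduled-only sentence directly follows one that names descriptive statistics, inference and derivations. The visible text does not define an emergent laboratory, vital-sign or ECG value. I take the usual meaning: out of range after vaccination and not before. Finding such a value means comparing post-dose with pre-dose values, which is a derivation. Nothing in 15.4.2 brings unscheduled values back in. The plain reading is that emergent values come from scheduled assessments only.

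**Step 2: what is scheduled in the primary window?** Section 15.4.2 states "Biochemistry and haematology tests will be performed at V1 (screening), V4 (part A), V5 (part B), V8 (parts A and B) and post-study medical visit", which is V10 in Part A and V20 in Part B. ECG is planned at screening and the post-study medical visit only. Days come from the Section 18 schedules.

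| Assessment | Part A, post-dose to Day 85 | Part B, post-dose to Day 85 | Next in Part B |
|---|---|---|---|
| Laboratory and urinalysis | Days 8, 43, 85 (3) | Days 15, 43 (2) | Day 365 |
| 12-lead ECG | Day 85 (1) | none (0) | Day 365 |
| Vital signs | Days 1, 2, 8, 43, 85, plus 29 and 30 if boosted | Days 1, 2, 15, 43, 57, 85, plus 29 and 30 if boosted | Day 113 |

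Visit windows do not change the ECG result. Section 12.4 allows ±3 weeks for Part B visits from Visit 11 onwards, so the earliest Visit 20 is Day 365 − 21 = Day 344, well after Day 85. In Part B, the last 85 − 43 = 42 days of the primary window contain no scheduled laboratory draw.

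**Step 3: where does an unscheduled out-of-range result go?**

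- If it is a deterioration that leads to symptoms, a change in treatment or discontinuation, Section 14.1 makes it an AE. If it is clinically significant and/or leads to medical intervention, Section 14.6 does so. It then enters the TEAE tables by group.
- If none of these applies, it is not an AE. It is outside the by-visit summaries and, on the reading in Step 1, outside the emergent listings. It remains in the general individual data listing of 15.1.1, which is not expressly limited to scheduled values.

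The affected results are therefore unscheduled, newly out of range, asymptomatic, untreated and judged not clinically significant.

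**Step 4: is the term scheduled settled?** Not for Day 1 vital signs. Section 15.4.2 gives 2 and 3 hours post-dose. Section 12.2.1 and the Part A schedule give 2 and 6 hours, while Section 12.2.2 and the Part B schedule give 2 hours. These must be reconciled before the rule can be applied to vital signs.

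**The case against.** The strongest reply is that exclusion from the listings is inferred. The paragraph concerns values used in statistics and derivations, whereas the emergent outputs are listings. A sponsor could say that the rule was meant only for by-visit summaries and tests. That reading is possible, but the text does not state it, and the paragraph names derivations. If it is the intended reading, one sentence would confirm it.

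The second reply is that other routes preserve the important results. This largely stands. The AE route covers symptoms, treatment change and intervention as well as clinical significance, and the individual data listing remains. What is lost is the narrow class in Step 3.

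Third, Section 15 defers detail to a SAP whose full text is not among the material reviewed. That SAP could resolve the point, but the rule as stated here would direct programming unless qualified.

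A reader might also infer three stronger points that the documents do not support:

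- **That emergent abnormalities are systematically under-counted by arm.** Section 15.4.2 plans no emergent count, worst-value table or shift table by arm, so no planned count is biased.
- **That the sparse schedule measures the damage.** The chance that a scheduled draw meets a short abnormality describes the schedule. Many abnormalities would never be sampled, with or without this rule.
- **That unscheduled tests are always prompted by a suspected problem, or that escalation decisions are affected.** Section 12.3 says only that they are at the Investigator's discretion, which includes repeat checks. The review in Section 12.5 uses eCRF data and transferred laboratory results, with no scheduled-only limit.

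**Conclusion.** The point holds in a limited form. As written, the scheduled-only rule makes the emergent-value listings of the primary safety endpoint less complete than they should be for laboratory tests, urinalysis, vital signs and ECG. Part B ECG needs no numerical assumption: there are 0 planned post-dose ECGs within 12 weeks, so on this reading any that is taken cannot contribute.

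The overall size cannot be calculated. It depends on how many unscheduled assessments are made and how many of their results are newly out of range without becoming AEs, and the documents give neither number. The conclusion rests on the plain reading of 15.1.1 and on the usual meaning of an emergent value. It does not imply that data are lost or that clinically significant findings go unreported.

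**What to change.** In Section 15.1.1, and in the detailed SAP to match, limit the rule and add the exception. Suggested wording:

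> By-visit summaries and statistical tests use scheduled post-vaccination values only. Emergent-value listings for laboratory tests, urinalysis, vital signs and ECG are derived from all post-vaccination values, scheduled and unscheduled, with unscheduled values flagged.

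Reconcile the Day 1 vital-sign times across Sections 12.2, 15.4.2 and 18, so that scheduled has one meaning. Worst-value shift tables by group would be a useful but optional addition, since the plan does not currently include them.

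The cost is wording and minor programming, with no new procedure for volunteers. The emergent listings may look slightly less favourable.

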15.1.2 Descriptive statistics for the two study parts

Descriptive statistics for quantitative parameters will be provided using number of observations (N), mean, standard deviation (SD), standard error of the mean (SEM), minimum, median and maximum. Descriptive statistics for qualitative parameters will be provided using absolute frequencies (n) and relative frequencies (%).

15.1.3 Inferential statistics

Adequate statistical tests will be used to carry out comparison between treatment/dose groups performed on primary, secondary or exploratory endpoints, even though it is accepted that the power of these tests for groups in Part A will be low due to small numbers of volunteers.

For categorical endpoints, such as local and systemic reactogenicity, a comparison of events intensity (scores) between vaccine dose groups will be performed with an adequate statistical test dealing with categorical variables (for example: Fisher exact test, Chi square test or generalized estimating equations).

For continuous endpoints, such as immune response induced by different GBS-NN vaccine dosing regimens, appropriate statistical method (for example: ANOVA) will be used to compare pre-vaccination and post-vaccination levels.

15.2 Studied populations for each study part

The following populations will be taken into account for each study part:

- **Intention to Treat Set (ITT):** All included volunteers who receive at least one dose of the study vaccine will be taken into account in the description of the population (disposition, demographic or baseline characteristics);
- **Immunogenicity Set (IG):** The subset of volunteers who will receive at least one dose of the study vaccine with available pre- and post-vaccination titers.
- **Per Protocol Set (PP):** All volunteers who receive both doses of the study vaccine and provide evaluable samples for analysis of the primary immunological endpoint and do not violate the protocol.

The Primary and Secondary Safety analyses will be performed on the ITT set. The Secondary Immunological analyses will be performed on the IG set. The “primary” immunological analysis (i.e. the results on Day 85 in both study parts) will also be performed on the PP set.

Missing or incomplete data will not be replaced, unless otherwise specified (example: values strictly under the LLOQ for immunogenicity data).

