For categorical endpoints, such as local and systemic reactogenicity, a comparison of events intensity (scores) between vaccine dose groups can be performed with an adequate statistical test dealing with categorical variables (for example: Fisher exact test, Chi square test or generalized estimating equations).

For continuous endpoints, such as immune response induced by different GBS-NN vaccine dosing regimens, appropriate statistical method (for example: ANOVA) can be used to compare pre-vaccination and post-vaccination levels.

Studied populations

The following populations will be taken into account for each study part:

- **Intention to Treat Set (ITT):** All included volunteers who receive at least one dose of the study vaccine will be taken into account in the description of the population (disposition, demographic or baseline characteristics);
- **Immunogenicity Set (IG):** The subset of volunteers who will receive at least one dose of the study vaccine with available pre- and post-vaccination titers.
- **Per Protocol Set (PP):** All volunteers who receive both doses of the study vaccine and provide evaluable samples for analysis of the

	
[REDACTED]
 
The Primary and Secondary Safety analyses will be performed on the ITT set. The Secondary Immunological analyses will be performed on the IG set. The “primary” immunological analysis (i.e. the results on Day 85 in both study parts) will also be performed on the PP set.
 
Sample size:
 
Up to 70 healthy female volunteers in part A (7 cohorts of 10 volunteers) and up to 240 in part B (3 cohorts of 80 volunteers). The final number of volunteers to be randomized in part B will be calculated following a data review from part A.

--	--

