It is anticipated that the results from Part A will indicate whether the optimal dose level lies between 10µg and 50µg, or between 50µg and 250µg. The effect of Alhydrogel® on these parameters will guide the decision on whether to include it in one or more cohorts in Part B.

Part B:

The levels of GBS-NN specific IgG observed in Part A at Day 57, along with the safety profile, will be used to define a narrower range of dose levels to explore in Part B, where the group sizes are larger and the significance of any observed differences in immune responses will be measurable.

It is currently anticipated that three dose regimens will be selected for evaluation in Part B. At least two dose levels will be evaluated, which may be the same or different to those administered in Part A, but will not exceed the highest dose administered in Part A. It is anticipated that the regimens in Part B will comprise two doses of Alhydrogel® adjuvanted vaccine with the second being administered after a variable interval, not exceeding four weeks. It is, however, possible that a single dose of vaccine may be evaluated in Part B.

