12.2 Treatment Period and Post-Study Period

12.2.1 Part A

Volunteers will receive one of up to 7 dosing regimens of GBS-NN or placebo on 1 or 2 occasions – a primary dose will be administered at Visit 2 and volunteers will remain in the study unit for at least 8 hours post-dose, and if a booster dose is required, this will be administered at Visit 6. There will be a time interval of 4 weeks between Visit 2 and Visit 6, although this time interval may change if the dosing regimen is changed. There will be 10 volunteers in each group, 8 randomised to active and 2 to placebo. All cohorts in Part A will incorporate sentinel dosing of 2 volunteers in each cohort for the primary dose only: 1 on active treatment and 1 on placebo. No further volunteers in that cohort will be dosed until at least 24 hours after dosing the second volunteer, provided that there are no serious or unexplained safety issues as determined by the Investigator.

The decision to proceed with administration of the primary dose in subsequent cohorts will be made as described in Section 12.5.

The following assessments will be carried out at these visits:

Visit 2

A urine pregnancy test, brief physical examination, urine drugs of abuse test and alcohol breath test will be performed to confirm eligibility. Eligible volunteers will be randomised to receive active or placebo on 1 or 2 occasions (all volunteers will receive a primary dose at Visit 2 and a booster dose of the same medication (active or placebo) will be administered at Visit 6 if required). The dose administered, the number of doses and the time interval between doses will be dependent on the data generated from the preceding cohort and will be decided by the Safety Review Committee. A pharmacodynamic blood sample will be taken to measure pre-existing antibody levels prior to dosing. The primary dose will be administered at Visit 2 and volunteers will remain in the study unit for at least 8 hours post-dose. Vital signs will be recorded pre-dose and at 2 and 6 hours post-dose. A brief medical examination (including an assessment of the injection site) will be performed prior to discharge to ensure the volunteer is fit for discharge.

Visit 3

Visit 3 will be performed 24 hours (\pm 2 hours) after administration of the primary dose and an assessment of the injection site will be performed, vital signs will be recorded and AEs and concomitant medications will be reviewed.

Visit 4

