Visit 4 will be performed 1 week after administration of the primary dose. An assessment of the injection site will be performed, vital signs will be recorded, safety blood samples for haematology and biochemistry will be collected, urinalysis will be performed and AEs and concomitant medications will be reviewed.

Visit 5

Visit 5 will be performed 2 weeks after administration of the primary dose. This visit will be performed via telephone and a review of AEs and concomitant medications will be performed.

Visit 6

Visit 6 will be performed 4 weeks after Visit 2. A booster dose will or will not be administered at this visit depending on the decision made by the Safety Review Committee for each cohort.

If a booster dose is administered at this visit, the following assessments will be performed: an assessment of the injection site and a pharmacodynamic blood sample will be taken to measure antibody response prior to dosing. A urine pregnancy test will be performed prior to dosing. A booster dose will be administered. Volunteers will remain in the study unit for at least 4 hours post-dose. Vital signs will be recorded pre-dose and at 2 hours post-dose. A brief medical examination (including an assessment of the injection sites) will be performed prior to discharge to ensure the volunteer is fit for discharge.

If a booster dose is not administered at this visit, the following assessments will be performed: an assessment of the injection site and a pharmacodynamic blood sample will be taken to measure antibody response.

AEs and concomitant medications will be reviewed whether a booster dose is administered or not.

Visit 7 (Only if a booster dose is administered)

Visit 7 will be performed 24 hours (\pm 2 hours) after administration of the booster dose and an assessment of the injection sites will be performed, vital signs will be recorded and AEs and concomitant medications will be reviewed. If a booster dose is not administered, this visit will not be performed.

Visit 8

Visit 8 will be performed 2 weeks following Visit 6 and the following assessments will be performed: an assessment of the injection sites, vital signs will be recorded, safety blood samples for haematology and biochemistry will be collected, urinalysis will be performed, a pharmacodynamic blood sample will be taken to measure antibody response and AEs and concomitant medications will be reviewed.

Visit 9

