12.2.2 Part B

Volunteers will receive one of 3 dosing regimens (X, Y or Z) of GBS-NN or placebo on 1 or 2 occasions – a primary dose will be administered at Visit 2, and if a booster dose is required, this will be administered at Visit 6. There will be up to 80 volunteers in each group, up to 60 randomised to active vaccine and up to 20 to placebo.

The following assessments will be carried out at the visits during the Treatment Period:

Visit 2

A urine pregnancy test, brief physical examination, urine drugs of abuse test and alcohol breath test will be performed to confirm eligibility. Eligible volunteers will be randomised to receive active or placebo on 1 or 2 occasions (all volunteers will receive a primary dose at Visit 2 and a booster dose will be administered at Visit 6 if required). The dose administered and the number of doses will be decided based on the results of Part A. Vaginal and rectal swabs will be taken to assess colonisation by Group B streptococcus (GBS) and a pharmacodynamic blood sample will be taken to measure pre-existing antibody levels prior to dosing.

The primary dose will be administered at Visit 2 and volunteers will remain in the study unit for at least 2 hours post-dose. Vital signs will be recorded pre-dose and at 2 hours post-dose. A brief medical examination (including an assessment of the injection site) will be performed prior to discharge to ensure the volunteer is fit for discharge.

Visit 3

Visit 3 will be performed 24 hours (\pm 2 hours) after administration of the primary dose and an assessment of the injection site will be performed, and vital signs will be recorded and AEs and concomitant medications will be reviewed.

Visit 4

Visit 4 will be performed 1 week after administration of the primary dose by telephone to review AEs and concomitant medications.

Visit 5

Visit 5 will be performed 2 weeks after administration of the primary dose and the following assessments will be performed: an assessment of the injection site, and AEs and concomitant medications will be reviewed, a pharmacodynamic blood sample will be taken to measure antibody response. Vital signs will be recorded, safety blood samples for haematology and biochemistry will be collected and urinalysis will be performed.

Visit 6

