Visit 6 will be performed 4 weeks after Visit 2, although this time interval may change depending on the dose regime chosen. A booster dose will or will not be administered at this visit depending on the dose regime chosen.

If a booster dose is administered at this visit, the following assessments will be performed: an assessment of the injection site, vaginal and rectal swabs will be taken to assess colonisation by GBS and a pharmacodynamic blood sample will be taken to measure

antibody response prior to dosing. A urine pregnancy test will be performed prior to dosing. A booster dose will be administered. Volunteers will remain in the study unit for at least 2 hours post-dose. Vital signs will be recorded pre-dose and at 2 hours post-dose. A brief medical examination (including an assessment of the injection sites) will be performed prior to discharge to ensure the volunteer is fit for discharge.

If a booster dose is not administered at this visit, the following assessments will be performed: an assessment of the injection site, vaginal and rectal swabs will be taken to assess colonisation by GBS and a pharmacodynamic blood sample will be taken to measure antibody response.

AEs and concomitant medications will be reviewed whether a booster vaccination is administered or not.

Visit 7 (To be conducted only if a booster dose is administered)

Visit 7 will be performed 24 hours (\pm 2 hours) after administration of the booster dose and an assessment of the injection sites will be performed, vital signs will be recorded and AEs and concomitant medications will be reviewed. If a booster dose is not administered, this visit will not be performed.

Visit 8

Visit 8 will be performed 2 weeks after Visit 6 and the following assessments will be performed: an assessment of the injection sites, vital signs will be recorded, safety blood samples for haematology and biochemistry will be collected, urinalysis will be performed, a pharmacodynamic blood sample will be taken to measure antibody response and AEs and concomitant medications will be reviewed.

Visits 9 and 10

These are follow-up visits for the assessment of pharmacodynamic markers and/or safety up to the timing of the primary endpoint (Visit 10 i.e. Week 12).

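### The Per Protocol set requires two doses, so a one-dose regimen, which the protocol permits, would have no Day 85 Per Protocol result

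*Combined protocol and SAP*

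**What the plan says.** Section 15.2 admits to the PP set "All volunteers who receive both doses of the study vaccine and provide evaluable samples for analysis of the primary immunological endpoint", and adds that they must not have violated the protocol. The synopsis carries the same condition as far as its text is visible: "All volunteers who receive both doses of the study vaccine and provide evaluable samples for analysis of the". Section 15.2 then states that the so-called primary "immunological analysis (i.e. the results on Day 85 in both study parts) will also be performed on the PP set". The main analysis of the secondary immunological endpoints is on the IG set, which needs at least one dose and titres before and after vaccination.

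Elsewhere the number of doses is left open.

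- **Part A, section 12.2.1, Visit 2:** "The dose administered, the number of doses and the time interval between doses will be dependent on the data generated from the preceding cohort".
- **Part A, section 12.2.1, Visit 6:** "A booster dose will or will not be administered at this visit depending on the decision made by the Safety Review Committee", and this is decided for each cohort.
- **Part A, section 10.1:** the schedule of optional cohort 7 is still to be determined.
- **Part B, section 10.1:** "It is, however, possible that a single dose of vaccine may be evaluated in Part B".
- **Part B, section 12.2.2:** "Volunteers will receive one of 3 dosing regimens (X, Y or Z) of GBS-NN or placebo on 1 or 2 occasions", and at Visit 6 "A booster dose will or will not be administered at this visit depending on the dose regime chosen".

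The anticipated plan is two doses throughout. Cohorts 1 to 6 of Part A are all scheduled for Days 1 and 29, and section 10.1 expects two-dose regimens in Part B.

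**The concern.** A PP set is meant to hold the volunteers who followed the plan. Under this definition, a regimen planned with one dose would have every adherent volunteer excluded. The other operative sections provide for a regimen without a booster. The schedules in section 18 drop Visit 7 and the Visit 6 vital signs and pregnancy test, and section 15.4.1 drops the Visit 6 pregnancy test. Only the PP definition has no provision for it.

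If a one-dose regimen were chosen, it would have no Day 85 PP estimate and no PP comparison with placebo or with another regimen. Its Day 29 versus Day 85 comparison would also be lost in PP. The PP placebo group would lose that cohort's placebo recipients, which makes the remaining comparisons with placebo less precise.

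Timing matters too. Under section 10.4, dedicated statistical staff are unblinded after the Week 12 soft lock, which is when the Day 85 analysis is done. Whether a one-dose regimen belongs in PP should not be left to interpretation at that stage.

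**Working it through.** The plan gives no figure for PP membership, significance level, power or effect size, so there is nothing of its own to reproduce. The check is a reading of the text followed by head counts.

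**1. Can a one-dose volunteer satisfy the definition?** Only if a second injection is given anyway. None is described. Section 12.2.1 says any booster is the same medication as the first injection, given if required. The section 18 footnotes give the booster only where it applies to the cohort. So every one-dose regimen has PP n = 0.

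**2. Part B head count.** Section 12.2.2 gives up to 80 per group, 60 active and 20 placebo, in three groups. With k one-dose regimens, the maximum PP membership is 60 × (3 − k) active and 80 × (3 − k) in total:

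| One-dose regimens, k | PP active (of 180) | PP total (of 240) |
|---|---|---|
| 0 | 180 | 240 |
| 1 | 120 | 160 |
| 2 | 60 | 80 |
| 3 | 0 | 0 |

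The totals assume that placebo recipients follow their cohort's schedule.

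**3. Part B comparisons.** Section 15.4.4 lists placebo against three regimens (3) and three pairs of regimens (3), so 3 + 3 = 6. A given regimen appears in 1 + 2 = 3 of them. Section 15.4.4 names Day 84 for these comparisons; this is read as the Day 85 visit.

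**4. Part B precision, one one-dose regimen.** With a common SD, the standard error of a difference is proportional to √(1/n₁ + 1/n₂). Pooled placebo falls from 3 × 20 = 60 to 2 × 20 = 40, against 60 active:

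√(1/60 + 1/40) / √(1/60 + 1/60) = √(0.04167 / 0.03333) = √1.25 = 1.118

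This is about 12% larger. The ratio is the same at any Part B size with 3:1 allocation. With m active per regimen, placebo falls from m to 2m/3, and the ratio is √(2.5/2) = √1.25.

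**5. Part A, one of cohorts 1 to 6 with one dose.** Each cohort has 8 active and 2 placebo, so 10 volunteers are excluded. Section 15.4.4 lists:

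- placebo against six groups: 6
- with against without Alhydrogel at three doses: 3
- dose pairs without Alhydrogel: 3
- dose pairs with Alhydrogel: 3

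The total is 15. A given cohort appears in 1 + 1 + 2 = 4. Pooled placebo falls from 12 to 10, against 8 active:

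√(1/8 + 1/10) / √(1/8 + 1/12) = √(0.22500 / 0.20833) = √1.08 = 1.039

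This is about 4% larger.

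**6. Part A, cohort 7 with one dose.** Its volunteers would be excluded, but the 12 placebo recipients in section 15.4.4 correspond to six cohorts of 2 and would be intact. The comparisons among cohorts 1 to 6 would not change.

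**The case against.** The strongest case on the other side concerns likelihood and consequence rather than the reading of the text.

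- **Two doses are anticipated throughout.** If the study runs as expected, nothing is affected. This stands, and it makes the point conditional.
- **Little depends on PP.** The primary objective is safety, analysed on the ITT set. Immunogenicity is secondary and is analysed on IG, with PP as an addition at Day 85. Part B regimens are chosen on Day 57 antibody levels, and no sample-size statement rests on PP. In a one-dose regimen no booster can be missed, so a correctly defined PP set would differ from IG only by protocol violators and volunteers without an evaluable sample. This stands too, and keeps the point minor.
- **A fuller SAP could refine the definition.** The protocol defers detail to the SAP, and the combined document contains no separate SAP text beyond section 15. A later definition cannot be excluded, but it would leave the protocol contradicting it.
- **The precision figures depend on how placebo is handled.** The 12% needs placebo pooled across cohorts and given on each cohort's schedule. Section 15.4.4 refers to a single placebo group, and the Part B schedule footnote ties the booster to the cohort, so both are supported. Section 12.2.2 does not, however, repeat the Part A statement that the booster is the same medication, active or placebo. If placebo recipients in a one-dose regimen received two injections, the loss of precision would be nil. The fair range is 0 to 12%.
- **The Part A case modelled is the less likely one.** Cohorts 1 to 6 are scheduled for two doses, and only cohort 7 has an open schedule. That is correct, although section 12.2.1 still leaves the booster to a decision for each cohort.

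**Conclusion.** The PP definition is wrong as written, at minor severity. It is a stated rule that fails in a branch the protocol permits, and no section adapts it.

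- **All regimens two-dose:** no effect.
- **One Part B regimen one-dose:** up to 80 volunteers cannot enter PP, 3 of 6 between-group comparisons are lost there, and the standard error of each remaining comparison with placebo is up to about 12% larger.
- **One of Part A cohorts 1 to 6 one-dose:** 10 volunteers cannot enter PP, 4 of 15 between-group comparisons are lost there, and the standard error of comparisons with placebo is about 4% larger.
- **IG analysis:** unaffected in every case.

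These sizes assume a common SD, all other PP criteria met, Part B groups at their ceilings, placebo pooled, and placebo given on the cohort's schedule. That a one-dose regimen has no PP result needs none of these assumptions.

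**What to change.** In section 15.2 and in the synopsis, replace the two-dose condition with receipt of *all doses planned for the assigned regimen*, and leave the rest of the definition as it is. Carry the same wording into the SAP, before the Week 12 unblinding of statistical staff.

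The new wording lets an adherent one-dose volunteer into PP, and still excludes a volunteer on a two-dose regimen who missed the booster. A one-dose Part B regimen could then contribute up to 60 active volunteers (80 with its placebo) to the Day 85 PP analysis instead of none. A one-dose Part A cohort could contribute up to 8 active (10 with placebo).

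The cost is one phrase in two places. Conduct, sampling, the choice of regimen and the PP set for two-dose cohorts do not change.
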